9.3.4 Hemophagocytic lymphohistiocytosis

During postmarketing use, HLH has been reported in patients treated with alemtuzumab. Hemophagocytic lymphohistiocytosis is a life-threatening syndrome of pathologic immune activation characterized by clinical signs and symptoms of extreme systemic inflammation, including fever, swollen lymph nodes, bruising or skin rash. It is associated with high mortality rates if not recognized early and treated. Symptoms have been reported to occur within a few months to four years following the initiation of treatment. Patients who develop disease manifestations of pathologic immune activation should be evaluated immediately, and a diagnosis of HLH as well as referral of the patient to a specialist should be considered.

9.3.5 Physical examination and vital signs

Whenever possible, the same physician should perform the physical examination at all study visits. The findings of each examination will be recorded.

A standard physical examination for clinical and neurological assessments which includes examination of major body systems, height and body weight will be performed.

Physical examination and vital signs will be performed at screening, D-14 to D-7, M0/D1, M4, M8, M12, M15, M18, M21, M24/at EOTP; every 6 months safety monitoring phase, and at every relapse visit.

The following vital signs: respiratory rate, heart rate, systolic and diastolic blood pressure and body temperature, will be measured during each physical examination and at the following timepoints during alemtuzumab treatment:

- Before methylprednisolone infusion.
- At a time after methylprednisolone infusion and prior to alemtuzumab infusion.
- 1 hour after the start of alemtuzumab infusion and hourly during and after infusion, until 2 hours after infusion has ended or longer until stabilization.

Body temperature will be collected using the same method at each assessment for a given patient.

Blood pressure will be measured under standardized conditions using the same method at each assessment for a given patient. It will be determined at each study visit using a well calibrated apparatus. Both systolic and diastolic blood pressure must be recorded.

The date of the first menarche should be captured if applicable.

The Tanner stage ([Appendix E](#)) should be assessed until complete sexual maturity at the specified time points, see Study flowchart [Section 1.2](#) for further details.

The Tanner scale (also known as the Tanner stages I-V) is a scale of physical development in children, adolescents and adults (23, 24). The scale defines physical measurements of development based on external primary and secondary sex characteristics, such as the size of the breasts, genitalia, and development of pubic hair. Tanner scale is performed either at the study site by the paediatric neurologist or paediatrician or at a designated site arranged by the Investigator.

9.3.6 Other safety endpoints

The other safety endpoints will be assessed by:

- Antidrug antibody formation (ADA).

Assessment of ADA formation will be performed at M0/D1 (baseline), post dose, M1, M3, M12 (prenext dose), M13, M15, M24/at EOTP, and annually in the safety monitoring phase.

IV infusion of alemtuzumab has been associated with the development of antialemtuzumab antibodies and inhibitory antibodies. Serum samples will be tested by established assay methods for the presence of antialemtuzumab antibodies and titers will be quantified for positive samples.

9.4 EXPLORATORY ENDPOINT

T1 weighted lesions and brain volume will be assessed on MRI as an exploratory endpoint MRI throughout the study period.

9.5 FUTURE USE OF SAMPLES

9.5.1 Immune markers (optional)

Based on the increased risk of autoimmune events observed with alemtuzumab, serum will be collected to support investigation of potential biomarkers predictive of the response to alemtuzumab. The markers to be tested may include cytokines and possibly other serum components; the specific markers to be assessed will be guided by results of ongoing biomarker investigations with alemtuzumab.

If the patient accepts to sign the specific informed consent form (ICF), “Future Use of Samples”, serum samples and peripheral blood mononuclear cell will be collected at the visit specified in the study flow chart (designated “immune markers”) and these samples will be stored to support future investigation of potential biomarkers predictive of autoimmunity, such as serum cytokines.

9.6 APPROPRIATENESS OF MEASUREMENTS

The primary endpoint is the number of new or enlarging T2 lesions during continuation of prior DMT (Period 1) and during an approximately equal period of time after Course 1 of alemtuzumab treatment (Period 2) This endpoint was agreed upon by the Paediatric Committee (PDCO) to protect the study population from any significant treatment-free period and provide an analysis of

an imaging biomarker for comparative purposes. The number of new or enlarging hyperintense lesions as detected by T2-weighted MRI has been used as a surrogate marker of efficacy in MS studies (25, 26). Cranial MRI will be performed at the times specified in [Section 1.2](#).

In the analysis of secondary endpoints, 4 primary areas will be prioritized. Safety and tolerability for up to 4 years after last dose of alemtuzumab will be assessed using descriptive statistics and evaluated in comparison to the adult data for the treatment of MS using alemtuzumab. Adverse events of special interest will be examined including the subsequent development of infusion-related reactions, events of autoimmunity particularly thyroid, ITP and nephropathies; serious infections. Certain exclusion criteria related to prior disease states associated with such reactions will be emphasized during screening. Routine lab monitoring during the course of the study and followup over 4 years following last infusion is planned.

EDSS score changes occurring following Period 1 will be analyzed. The EDSS will be performed by the neurologist at the following visits: Screening, Day-14 to Day -7, Months 4, 8, 12, 15, 18, 21, and 24/at EOTP, every 6 months in the safety monitoring phase, and at every relapse visit. The EDSS has long been considered the standard for assessing disability in patients with MS (27, 28).

The annualized relapse rate (ARR) will be assessed at Year 2. The annualized relapse rate is widely used and generally accepted as an indicator of the efficacy of drugs to reduce cerebral inflammation in MS studies (27, 28).

Cognition test scores (BVMT-R and SDMT) will be tested over 2 years. Cognitive decline is recognized as a prevalent and debilitating symptom of multiple sclerosis (MS), especially deficits in episodic memory and processing speed. The change from baseline in cognitive outcomes are to be analysed descriptively. The SDMT is a test of speed that screens for organic cerebral dysfunction and has been validated and used in numerous MS clinical trials (29, 30). The BVMT-R is a test of memory that has been validated in MS and has been used in clinical trials (31). Quality of life measures will be assessed using the validated pediatric Neuro-QOL which will be measured at least every 6 months over 2 years. This measure assesses how disease and health factors affects children's lives (32).

10 STUDY PROCEDURES

All the study procedures will be performed following the standard clinical practice of each study center. Refer to the [Section 1.2](#) for more details.

10.1 VISIT SCHEDULE

The visit schedule consists of the following visits:

10.1.1 Visit 1 Screening visit

This visit has to be conducted maximum 28 days prior to M-4 visit.

Prior to any assessments, information for the parents/patient regarding the aims and methods of the study, its constraints and risks, and educational material consistent with the risk management plan for alemtuzumab will be reviewed with the parents/patient and a written summary in the form of an informed consent will be given to the parents/patient.

The patient/patient's legal guardian must sign the informed consent/assent prior to any action related to the study.

The screening visit will include the following investigations (refer to [Section 1.2.1](#)):

- Recording of medical/surgical history.
- **Physical examination and vital signs:** A standard physical examination for clinical and neurological assessments which includes examination of major body systems, height and body weight. Tanner stage will be assessed as well.
- The following vital signs will be recorded: systolic and diastolic blood pressure (millimeters of mercury [mm Hg]), heart rate (beats/minute), respiratory rate (breaths/minute), and temperature (degrees Celsius [°C] or degrees Fahrenheit [°F]).
- **Demographics** (gender, age, and race).
- Recording of prior MS medications and concomitant medications.
- **Laboratory screening:**
 - Hematology (CBC with differential, including platelet count for monitoring for any cytopenia),
 - Chemistry panel: Glucose, creatinine, blood urea nitrogen (BUN), sodium, potassium, chloride, bicarbonate, magnesium, calcium uric acid, aspartate aminotransferase, ALT, gamma-glutamyl transpeptidase (GGT), lactate dehydrogenase, total bilirubin, direct/indirect bilirubin, alkaline phosphatase, inorganic phosphorus, total protein, albumin, globulin, albumin/globulin ratio, triglycerides, cholesterol and creatinine phosphokinase will be assessed,
 - Thyroid function testing (thyroid stimulating hormone),

- Serology tests: hepatitis B/C and HPV. Other serology test may be required according the patient vaccination status,
 - Urinalysis (pH, ketones, cells, protein, glucose, blood, urobilinogen, bilirubin, microscopic sediment, specific gravity),
 - TB testing (as per local practice),
 - For women: Beta human chorionic gonadotropin pregnancy test for women of childbearing potential, who have commenced menstruating.
- Blood sample collection for lymphocyte phenotyping.
 - Perform MRI scan without contrast. It is important to ensure that this MRI assessment is performed 4 months (± 7 days) apart to the MRI assessment on D-7 visit. The MRI assessments will be available to investigators to assess safety.
 - Perform EDSS assessment.
 - Perform SDMT and BVMT-R test.
 - Recording of PedsQL/Ped NeuroQoL.
 - Remind patient to continue on their DMT.
 - Commence AE/SAE reporting.

Note: The above investigations may be performed on separate visits as long as all are completed within the 28 days prior to inclusion (V2, M-4). If any of the examinations/measurements does not fulfill the inclusion/exclusion criteria at the screening visit, they may be repeated before Visit 2.

10.1.2 Visit 2/(M-4) study eligibility confirmation visit

The following items will be checked/performed and recorded for all patients:

- Review any potential AEs/SAEs and concomitant medication used since Visit 1.
- Review/confirm eligibility criteria based on review of inclusion/exclusion criteria.

Only patients who meet all the inclusion criteria and none of the exclusion criteria will be included in the study. Each patient will receive an incremental identification number corresponding to his/her order of enrollment in the study.

- If the patients do not meet eligibility criteria, they will be considered screen failures. These patients may be re-assessed and included in the study if they meet all eligibility criteria,
- After this visit, during DMT phase until Day -7 visit, Investigator or designee will perform monthly phone calls to remind patients and parents about continuation of DMT and check patient status.

10.1.3 Visit 3/Days -14 to -7

Visit 3 assessments can be performed over multiple days as long the time windows below are respected.

The following items will be checked/performed and recorded for all patients:

- Perform MRI scan without contrast. It is important to ensure that this MRI assessment is performed 4 months (± 7 days) from the MRI assessment done at screening.
- Physical examination including vital signs.
- AEs/SAEs (if any) will be monitored.
- Concomitant medication (if any) will be checked and reported.
- Blood and urine sample for laboratory assessments (hematology and chemistry) including thyroid function test; pregnancy test (for females of childbearing potential), and urinalysis will be collected at Day -14 in order that results can be available at the latest on Day -7.
- Check for prior DMT compliance.
- Perform EDSS assessment.
- Perform SDMT and BVMT-R test.
- Recording of PedsQL/Ped NeuroQoL.
- Day -7 (phone call or visit): The Investigator will assess and confirm eligibility for alemtuzumab administration. If the patient is eligible for alemtuzumab administration, the prior DMT will be discontinued.

Premedication will be given to the patient and patient will be instructed to take premedication the day prior to the alemtuzumab administration in the morning and in the evening according to the schedule. Refer to [Section 8.2](#) for further details.

10.1.4 Visit 4/M0/D1 (first course of alemtuzumab)

Alemtuzumab treatment must be initiated and supervised by a neurologist experienced in the treatment of patients with MS. Specialists and equipment required for the timely diagnosis and management of the most frequent adverse reactions, especially autoimmune conditions and infections, must be available.

During the alemtuzumab infusion days, patients are not required to stay hospitalized overnight; however it remains at Investigator's discretion to decide if patient needs to be hospitalized during infusion periods.

Observation for infusion reactions is recommended during and for at least 2 hours (based on local requirements) after alemtuzumab infusion.

The day prior to first alemtuzumab administration patient should take the premedication as specified in [Section 1.2.1](#) and [Section 8.2](#).

On days of alemtuzumab infusion, and 1 hour prior to the infusion, H1 antagonist IV should be administered immediately followed by 1000mg IV methylprednisolone (whichever is lower), on the first 3 days of alemtuzumab administration and ≥ 500 mg on infusion Days 4 and 5. H2 antagonist medications and NSAID/antipyretic should be administered on the 5 days of alemtuzumab administration as needed. Study patients should also receive antiviral prophylaxis for herpetic viral infection beginning on Day 1 and continuing for a minimum of 1 month. If diphenhydramine IV is not available, an equivalent H1 antagonist can be used at an equivalent dosing, via IV route. If no H1 antagonist is available in IV formulation, an oral formulation of an equivalent compound can be used at an equivalent dosing, 2 hours prior to infusion.

Alemtuzumab will be administered as daily IV infusion on 5 consecutive days in a supervised medical setting. Calculation of the dose used will be based on patient weight. Vital signs during infusion days will be monitored.

The following assessments should be done as listed in the study flow chart (refer to [Section 1.2.1](#)):

- Physical examination and vital signs.
- Check for compliance.
- Preinfusion blood samples collection for clinical laboratory assessments and for ADA.
- Blood sample collection for serum creatinine and ALT.
- Blood samples collection for immune markers (optional) and PK.
- AE/SAE will be monitored (if any).
- Concomitant medication will be checked and reported (if any).
- The Investigator or designee will contact the IVRS to obtain a treatment kit number.

The following infusion management procedures must be utilized for each infusion and each treatment course:

- Pre-infusion : Physicians should obtain a baseline ECG and vital signs (including heart rate and blood pressure measurement), screen for pre-existing hemorrhagic, cardiovascular (including venous thromboembolism) and cerebrovascular risk factors, screen for lung disease, review concomitant medications (eg, antiplatelet agents, anticoagulants), perform laboratory tests (complete blood count with differential, serum transaminases, serum creatinine, test of thyroid function and urinalysis with microscopy), and evaluate infusion-related risks. Physician should also apply the following contraindications when treating patients in this study:
 - Hypersensitivity to the active substance, or to any of the excipients
 - Human Immunodeficiency Virus (HIV) infection
 - Severe active infection
 - Uncontrolled hypertension
 - History of arterial dissection of the cervicocephalic arteries
 - History of stroke
 - History of angina pectoris or myocardial infarction
 - Known coagulopathy or on concomitant anti-coagulant therapy

It is at investigator's discretion to treat or not treat patient with alemtuzumab after clinical evaluation.

- During infusion: Continuous/frequent monitoring of heart rate, blood pressure assessment (at least hourly) and overall clinical status of the patients including consideration of the volume of fluids administered. The following are recommendations in case of clinical abnormalities/severe adverse event:
 - Interrupt infusion
 - Medically evaluate the patient guided by the adverse event profile of alemtuzumab prior to considering restarting therapy
 - Provide appropriate treatment as needed
 - Consider permanently discontinuing the alemtuzumab infusion if the patient shows clinical symptoms suggesting development of a serious adverse event associated with the infusion (myocardial ischemia, hemorrhagic stroke, cervico-cephalic arterial dissection or pulmonary alveolar hemorrhage).
 - Implement appropriate measures for patients at risk of venous thromboembolism: repeated ambulation during infusion and/or compression stockings.

- Post-infusion: Observation and education of patients
 - Observation for infusion reactions is recommended for a minimum of 2 hours after alemtuzumab infusion; 2 hours after infusion, patients should be cautious and reporting if any of the infusion reactions develop within 48 hours.
 - Patients with clinical symptoms suggesting development of a serious adverse event temporarily associated with the infusion (myocardial ischemia, hemorrhagic stroke, cervico-cephalic arterial dissection or pulmonary alveolar hemorrhage) should be closely monitored until complete resolution of the symptoms. The observation time should be extended as appropriate.
 - Patients with persistent blood pressure elevation should be referred to an appropriate medical facility for continued monitoring and treatment.
 - The patients should be educated on the potential for delayed onset of infusion associated reactions and symptoms and signs of cardiovascular or cerebrovascular events, and instructed to report symptoms and/or seek appropriate medical care.

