patients were nasopharyngitis, urinary tract infections (UTI), upper respiratory tract infections (uRTI), sinusitis, influenza, bronchitis, oral herpes and herpes zoster. Prophylactic acyclovir treatment was used effectively in the clinical studies to reduce risk of Herpes Simplex virus infection (HSV) and therefore patients should receive concomitant acyclovir starting on the first day of any alemtuzumab course and continuing for at least 1 month after the last day of the course. Preservation of innate immunity and relative sparing of memory lymphocytes, together with the preservation of serum immunoglobulins (14), may contribute to the relatively low rate of serious infections following alemtuzumab treatment in MS patients.

During the course of the clinical studies, malignancies were observed in both alemtuzumab- and IFNB-1a-treated patients. However, the annualized rates of malignancy were similar across all treatment groups, and moreover, the malignancy risk was similar to the background incidence in the general population. The risk of malignancy will be further investigated in a long-term observational study.

As previously mentioned, the identified risks of alemtuzumab in patients with RRMS include:

- IARs (including cerebrovascular, cardiovascular, and pulmonary alveolar hemorrhage events).
- Serious infections.
- Autoimmunity (notably, ITP, thyroid disorders, or rarely nephropathies and autoimmune hepatitis, and hepatic injury).

Alemtuzumab Post-Marketing Updates in Adult

In post-marketing pharmacovigilance (PV) monitoring, infrequent cases of temporally associated pulmonary alveolar haemorrhage, myocardial ischemia, stroke (including ischemic and hemorrhagic stroke) and cervicocephalic (eg, vertebral, carotid) arterial dissection have been reported. Reactions may occur following any of the infusions during the treatment course. In the majority of cases time to onset was within 1-3 days of alemtuzumab infusion. Patients should be informed about the signs and symptoms, and advised to seek immediate medical attention if any of these symptoms occur.

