9.3.1 Adverse events

Adverse events reported by the patient or observed by the Investigator will be monitored, and include:

- Occurrence, seriousness, grade/intensity, relationship to study drug, resolution, and outcome of serious adverse event (SAE), adverse event of special interest (AESI), and AEs.
- Assessment of IARs: An IAR is defined as any AE occurring during alemtuzumab infusion or within the 24 hour post-infusion period. However, some IARs may occur beyond 24 hours (such as pulmonary alveolar hemorrhage, stroke, cervicocephalic arterial dissection, myocardial ischemia, thrombocytopenia and myocardial infarction). Toxicity grade (severity) of IAR is based on CTCAE. The timing of IAR in relation to alemtuzumab administration and distribution of IARs based on toxicity grade (severity) observed in the study for both study periods will be assessed.

Refer to [Section 10.4.1](#) for details.

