 - Patients with clinical symptoms suggesting development of a serious adverse event temporarily associated with the infusion (myocardial ischemia, hemorrhagic stroke, cervico-cephalic arterial dissection or pulmonary alveolar hemorrhage) should be closely monitored until complete resolution of the symptoms. The observation time should be extended as appropriate.
 - Patients with persistent blood pressure elevation should be referred to an appropriate medical facility for continued monitoring and treatment.
 - The patients should be educated on the potential for delayed onset of infusion associated reactions and symptoms and signs of cardiovascular or cerebrovascular events, and instructed to report symptoms and/or seek appropriate medical care.
- Perform MRI scan without contrast.
 - Perform EDSS assessment.
 - Perform SDMT and BVMT-R test.
 - Recording of PedsQL/Ped NeuroQoL.

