10.4.1.3 Adverse event of special interest

Any AESI will be reported to the Sponsor in the same timeframe as SAEs, ie, within 24 hours, as detailed in [Section 10.4.4](#).

An AESI is an AE (serious or nonserious) of scientific and medical concern specific to the Sponsor's product or program, for which ongoing monitoring and immediate notification by the Investigator to the Sponsor is required. Such events may require further investigation in order to characterize and understand them. Adverse events of special interest may be added, modified or removed during a study by protocol amendment.

The following AE will be considered as an AESI:

- Hypersensitivity or anaphylaxis.
- Pregnancy occurring in a female patient entered in the clinical trial. It will be qualified as an SAE only if it fulfills one of the seriousness criteria (see [Section 10.4.1.2](#)). Follow-up of the pregnancy in a female participant is mandatory until the outcome has been determined.
- Symptomatic overdose (serious or nonserious) with IMP/non-investigational medicinal product (NIMP).
 - An overdose (accidental or intentional) with the IMP is an event suspected by the Investigator or a nurse and defined as an increase of at least 30% of the dose to be administered in the specified duration or if the dose is administered in less than half the recommended duration of administration,
 - An overdose with the NIMP is an event suspected by the Investigator or spontaneously notified by the patient (not based on systematic pills count) and defined as at least twice the intended dose within the intended therapeutic interval, adjusted according to the tested drug,
 - Of note, asymptomatic overdose has to be reported as a standard AE.
- Increase in ALT (see the "Increase in ALT" flow diagram in [Appendix B](#) of the protocol).
- Other product specific AESI(s):
 - Autoimmune mediated conditions including but not limited to autoimmune encephalitis, cytopenias, ITP, autoimmune hepatitis, nephropathies including anti-glomerular basement membrane (GBM) disease, thyroid disorders and acquired Hemophilia A (see [Appendix B](#))
 - Temporally associated* pulmonary alveolar hemorrhage
 - Temporally associated* myocardial ischemia, myocardial infarction
 - Temporally associated* stroke
 - Temporally associated* cervicocephalic arterial dissection
(* Temporally associated: 1 to 3 days after the last infusion)
 - HLH,
 - Progressive multifocal leukoencephalopathy (PML)
 - Pneumonitis,

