11.4.3 Analyses of safety data

11.4.3.1 Adverse events

AE observation period:

- Pretreatment AEs are defined as those AEs that developed or worsened prior to the 1st alemtuzumab dose.
- On treatment AEs are defined as those AEs that developed or worsened after the 1st alemtuzumab dose and until the end of the study (Month 60).
- Posttreatment AEs are defined as those AEs that developed or worsened after the ontreatment period.

On-study period will include pretreatment and ontreatment period. Treatment emergent adverse events (TEAEs) for analysis purpose will include all ontreatment AEs.

The primary analysis of adverse event reporting will be on TEAEs. Pretreatment AEs will be summarized separately.

The incidence of TEAEs (including IARs), AESI, will also be tabulated (frequencies and percentages) by severity, grade/intensity, and relationship to study drug. In tabulating severity of AEs on a per patient basis, the greatest severity will be assigned to a patient when there is more than one occurrence of the same AE with different reported severities. Relationships of the AE to treatment will be categorized as not related, or related. The highest level of association will be reported in patients with differing relationships for the same AE. Actions taken regarding treatment and patient outcome will also be listed.

In addition to IARs analysis above, TEAEs that occurs from start of infusion up to 72 hours postinfusion will be summarized if applicable.

The incidence of AEs leading to study discontinuations will also be summarized by treatment group, with details provided in the listing.

Death: The following deaths summaries will be generated:

- Number (%) of patients who died by study period (TEAE, on-study) and reasons for death summarized on the safety population.
- TEAE leading to death (death as an outcome on the AE e-CRF page as reported by the Investigator) by primary system organ class (SOC), high level group term (HLGT), high level term (HLT) and preferred term (PT) showing number (%) of patients sorted by internationally agreed order of SOC and alphabetic order of HLGT, HLT, and PT.

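### The 48-hour patient-reporting period after infusion is 24 hours shorter than the protocol's own 1-3 day window for serious infusion-associated events: a minor alignment

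*Protocol*

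**What the plan says.** The post-infusion lists in Protocol 10.1.4 (first course) and 10.1.10 (second course) have the same content on this point. Each holds:

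- a site observation period of at least 2 hours after the infusion;
- one timed instruction to patients: "patients should be cautious and reporting if any of the infusion reactions develop within 48 hours";
- an untimed bullet under which patients are to be "educated on the potential for delayed onset of infusion associated reactions" and on cardiovascular and cerebrovascular warning signs, and are to be "instructed to report symptoms and/or seek appropriate medical care".

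Elsewhere the protocol uses three days for the serious events:

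- Section 4, on adult post-marketing reports of alveolar haemorrhage, myocardial ischaemia, stroke and cervicocephalic dissection: "In the majority of cases time to onset was within 1-3 days of alemtuzumab infusion". Patients are to be "advised to seek immediate medical attention if any of these symptoms occur", with no time limit.
- Section 10.4.1.3, repeated in Table 9 (10.4.6), for the same events as adverse events of special interest: "Temporally associated: 1 to 3 days after the last infusion".
- Section 11.4.3.1, a descriptive summary: "TEAEs that occurs from start of infusion up to 72 hours" after infusion.

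Section 9.3.1 defines an infusion-associated reaction (IAR) by a 24-hour limit, then adds that "some IARs may occur beyond 24 hours" and gives these same events as examples.

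**The concern.** The 48-hour sentence speaks of infusion reactions in general. Because 9.3.1 counts stroke, dissection, myocardial ischaemia and alveolar haemorrhage as such reactions, the sentence reaches them and cannot be set aside as meant only for rash or fever. For those events Section 4 gives clinical onset mostly over 1-3 days, so the one period addressed to patients stops before the protocol's own risk window does.

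The patients are children and adolescents who need not stay overnight on infusion days, so early recognition at home falls to the patient or a parent. The lists contain a single number for how long to stay alert, and a site preparing a leaflet or discharge advice is likely to copy it. The protocol gives no reason for a shorter period. Appendix I shows that the 48-hour text and the 1 to 3 day definition both came in with amended protocol 04, which suggests that the two were simply not matched.

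**Working it through.** **1. The limits side by side**

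| Place in Protocol | Purpose | Limit |
|---|---|---|
| 10.1.4 and 10.1.10, timed sentence | patient reporting | 48 h |
| 10.1.4 and 10.1.10, last post-infusion bullet | patient reporting, seeking care | none stated |
| Section 4 | clinical onset, most cases | 1-3 days |
| Section 4 | patient seeks immediate attention | none stated |
| 10.4.1.3 and Table 9 | definition of temporally associated event | 1-3 days after last infusion |
| 11.4.3.1 | descriptive summary | 72 h |

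**2. Size of the mismatch**

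- Upper end of the window: 3 days x 24 h = 72 h, which agrees with the 72 hours in 11.4.3.1.
- Shortfall of the timed instruction: 72 - 48 = 24 h, in both courses.
- The sentence does not fix its starting point. If the 48 hours run from the end of the 2-hour observation, the limit is 48 + 2 = 50 h after infusion and the shortfall is 72 - 50 = 22 h.

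**3. Where the shortfall falls**

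Infusions are on consecutive days. Hours 48-72 after any earlier infusion are hours 24-48 after the next one, and so still inside a 48-hour period. Only the last infusion of a course leaves an interval.

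- Course 1: last infusion Day 5; +48 h = Day 7; +72 h = Day 8.
- Course 2: last infusion Day 3; +48 h = Day 5; +72 h = Day 6.

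**4. Scheduled contact nearby**

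- Course 1: the next item in Table 4 is a PK sample on Day 14 ± 2, so Day 12 at the earliest; 12 - 8 = 4 days after the interval ends. The next visit is M1.
- Course 2: the next item in Table 5 is a PK sample on Day 12 ± 2, so Day 10 at the earliest; 10 - 6 = 4 days after the interval ends. The next visit is M13.

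Both samples are drawn at a local laboratory without a site visit where feasible. The Year 1 schedule (Table 1) is not in the text available, so the course 1 reading rests on 10.1.4, 10.1.5 and Table 4. These dates explain why recognition rests with the family. They do not enlarge the defect, because a longer reporting period adds no contact.

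**5. What the untimed text covers**

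The step through 9.3.1 that brings the serious events under the 48-hour sentence also brings them under the delayed-onset bullet. That bullet has no end point, so it applies at hours 48-72 and beyond, as does the advice in Section 4.

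**6. After the correction**

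With a period of at least 72 hours, the shortfall against 10.4.1.3 and 11.4.3.1 is 72 - 72 = 0 h.

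**The case against.** The strongest reply is that the gap is already closed. The untimed bullet in the same list tells patients about delayed reactions and tells them to report or seek care, and Section 4 says the same without a limit. Nothing in the 48-hour sentence tells anyone to stop reporting afterwards. This largely stands: hours 48-72 are covered in substance. It leaves standing that the only figure in the list is too short for the events that matter most.

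A second reply is that windows for classifying events, for tabulating them and for patient vigilance serve different purposes and need not agree; the basic IAR definition itself uses 24 hours. That is fair for 10.4.1.3, Table 9 and 11.4.3.1, none of which is addressed to patients. It does not answer Section 4, which describes when the events actually begin.

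A third is that 72 hours is no ceiling either, since Section 4 speaks only of most cases. This is correct, and it is why the new wording should say *at least* and why the untimed bullet should stay.

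Finally, 10.1.1 says educational material in line with the risk management plan is reviewed with families. It is not shown and may already give a longer period.

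A reader might infer that families are handed two conflicting deadlines. The documents do not support that: the text addressed to patients has one timed limit and one open-ended instruction. Nor can one infer that events at 48-72 hours would go unrecorded, since 10.4.3 has adverse events recorded from consent to the end of the study.

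**Conclusion.** The mismatch is real and minor. The timed patient-reporting instruction in 10.1.4 and 10.1.10 is 24 hours shorter than the protocol's own window for serious infusion-associated events (about 22 hours if counted from the end of observation), and this bites once per course, after the last infusion.

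The conclusion assumes that 9.3.1 brings these events within the infusion reactions named in the sentence, and that 3 days is read as 72 hours. It does not extend to a claim that patients lack instruction in that interval, or that a particular share of events would be recognised late: the documents give no distribution of onset times from which to compute one. The consequence is limited to the chance that a site passes the shorter number to families. Safety data and their analysis are not affected.

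**What to change.** In both 10.1.4 and 10.1.10, replace the 48-hour limit with *within at least 72 hours (3 days) after each infusion*. Keep the untimed delayed-onset bullet in each list so that 72 hours is not read as a cap, and check that the patient education material uses the same period. Leave adverse event recording, the definition in 10.4.1.3 and Table 9, and the summary in 11.4.3.1 as they are.

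The cost is one number in two sections and a check of the education text, with no added visits, tests or staff. Section 15 requires ethics committee approval before an amendment is implemented (overriding safety reasons aside), so this belongs with the next amendment and does not justify one of its own.
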